The present clinical study aims to verify the effectiveness and safety of the blue light photobiomodulation therapy with EmoLED medical device in supporting the reparative process of the area of the second and third stage decubitus lesion, comparing this method with the effectiveness of the therapy commonly used in the clinical field.

Ethical considerations

This Study will be conducted with reference to the standards of Good Clinical Practice and in accordance with the principles of the Declaration of Helsinki, with the UNI_ISO_14155_2020 norm, and with all relevant local laws and regulations, applicable to clinical trials that use patients as research object. This clinical investigation cannot begin in the involved center before having received the favorable written approval of the “Area Vasta Toscana Centro” Ethics Committee. The medical assistance provided to the subject is responsibility of adequately qualified doctors, as the center involved in this study is specialized in the treatment of the pathology object of the clinical trial.

During this trial, the patients' right to physical and mental integrity, the right to privacy and the protection of data concerning them will be respected in accordance with Directive 95/46 / EC.

This clinical investigation was designed to cause as little pain, discomfort, fear and other foreseeable risks for the subject as possible, and the degree of discomfort related to the trial itself or to the treatment with the medical device in question is almost nil, considering the Clinical Evaluation Report of the device and the safety data obtained from post-marketing surveillance.

The degree of discomfort / pain of the enrolled patients is however subject to continuous verification during the clinical trial, through a special questionnaire on the detection of discomfort connected to participating in the study in question. The risk / benefit ratio will be constantly checked throughout the trial, taking into account any adverse events / device-related accidents or non-serious side effects reported by the main investigators, and the preliminary assessment of the benefits about patients who have completed the study process.

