2. Safety of treatment (number of related adverse events in the two groups).

Measurable parameters

After enrolment and signature of the informed consent, the salient data, in the appropriate case report form, and the photographic images of the 2° and 3° stage injuries of each patient will be collected.

Three times a week (in conjunction with the dressing change) data, on patient forms, will be recorded, while once a week and at the last visit, if healing has not occurred before, the photographic images of each lesion of 2° and 3° stage will be captured.

All these variables will be measured during the 4-week observation period. The date of recovery, if it occurs before the end of the observation period, will be recorded in the patient’s case report form and the photographic image of the healed area will be acquired.

WEEK	W 1			W 2			W 3			W 4		
VISIT	V 1	V 2	V 3	V 4	V 5	V 6	V 7	V 8	V 9	V 10	V 11	V 12
CRF	P	P	P	P	P	P	P	P	P	P	P	P
PICTURE	P			P			P			P		P

Recording of clinical data

Data related to the evaluation of the endpoints are acquired during the visit for both study groups and will be inserted in pseudonymized form within a computerized database, where each subject will be associated with an alphanumeric identification code. The key of patient association code will be kept by the Principal Investigator for the duration of the study, it will not be communicated to the Sponsor and to the scientific coordinator and it will be eliminated at the end of the study, making the data completely anonymous.

The parameters of the Case Report Form and the photographic images of the lesions are both acquired and stored in digital format, during the length of the clinical trial and afterwards, for 10 years after the conclusion of the study.

Once the storage period indicated above has expired, the data will be anonymized so that it is no longer possible to trace, directly or indirectly, the identity of the interested subject. Anonymized data may be reused for further research and may therefore be stored indefinitely.

Each photograph of the lesions will be identified only with the patient code and the date of the visit.

The analysis of the photographic images will be performed through an appropriate analysis algorithm that measures in mm² the surface of the lesion.

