In addition, the data collected with the CRF, and other data from the medical records of patients enrolled, will be grouped and reported, in pseudonymized form, in a computerized database on three forms, generated with Forms of Microsoft, which will be filled by the health care personnel of the study team of the Experimental Center and which will be accessible to EMOLED staff of the Clinical Affairs Area. Specifically: in the Form "Patient Card", to be filled in during the enlistment phase, general clinical information is collected (alphanumeric ID associated with the enlisted patient, anamnesis, check of inclusion/exclusion criteria, Braden scale, etc.); in the Form "Patient Card Integration", also to be completed during the enlistment phase, are reported comorbidity, drug therapies and any allergies; while in the last Form "Patient Visit" the data relating to each of the three weekly visits provided for by the protocol are entered, namely those relating to the parameters of the PUSH scale (size of the lesion, exudate and type of tissue), the dressings and any notes.

The Braden scale, present in the Form "Patient Card", is used to assess the risk of the onset of pressure ulcers and, in particular for patients in prolonged stay or who are not able to move in total autonomy, is an assessment to be repeated at least once a week. The Braden scale takes into account 6 factors: sensory perception (ability to respond to discomfort dictated by compression), moisture of the skin (sweating, moisture linked to possible urinary and/ or fecal incontinence), motor activity (level of physical activity), mobility (ability to control/change the position of the body), nutrition (an adequate intake of calories, proteins, vitamins and minerals is essential to prevent the onset of new lesions) and, finally, friction and slipping (the friction force created with the solid surface and/or the linen can accelerate the onset of PU). Variables are ascribed to each factor and it is interpreted according to the principle that the lower the value resulting from the sum of all scores, the higher the risk of injury.

In the mentioned forms, the anonymity of patients will be guaranteed through the association of the patient's sensitive data with a progressive numerical ID. The register of this association will be accessible only to the medical staff of the structure that is part of the study team.

Photographic images acquisition

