A total of 40 "evaluable" patients will be recruited in total, 20 patients with second stage PU and 20 patients with third stage PU, 10 per arm (Treated and Controlled) within each group, at the facility involved in this Clinical Study. By "evaluable" patient it is meant a patient enrolled who has respected the temporal sequence of treatments as indicated in this protocol. The expected time for enrollment is 10 months. However, the study will continue until the number of patients required by this protocol is reached.

Enrollment point

Once the patient has signed the Informed Consent, the Principal Investigator enters the data in the Enrollment Register, scrupulously checking all the inclusion and exclusion criteria; if all the criteria

are met, the patient is considered enrolled in the clinical trial and subsequently randomized.

Number of experimental medical devices expected to be used

Each experimental site will be equipped with a v.1 EmoLED medical device.

Time-frame of the study

The Study has an indicative duration of 12 months with an expected enrollment period of 10 months. The study, however, will continue until the number of patients required by this protocol is reached.

¹ The state of pregnancy or breastfeeding will be certified on the basis of the patient's declaration.

Medical and surgical procedures and study follow-up

The Control Group will follow the standard treatment indicated three times a week for the 4 weeks of observation. The experimental group will undergo, in addition to the standard treatment, treatment with Emoled three times a week for 4 consecutive weeks.

This treatment consists of irradiation with the blue light emitted by the device for one minute on the injured area. If the lesion has a greater extension than the irradiated area, multiple repeated applications will be performed, on adjacent areas, until the entire area is covered.

The treatment with EmoLED will be carried out in correspondence with the dressing change of the lesion.

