For the purposes of this clinical trial, the data referred to in Article 4 No. 1 of the GDPR and data falling into the "particular" categories of personal data, in particular health data referred to in Article 9 of the GDPR, will be processed. The Principal Investigator is identified by the involved investigator site as an authorized person to be treated in accordance with Article 29 of the GDPR, as a person designated in accordance with Article 2 quaterdecies of the Code, and must acquire from the patient duly informed the consent document as well as to participate in the trial, also to the processing of data, after having informed clearly and completely, before the trial begins, each patient about the nature, purpose, results, consequences, risks and methods of processing personal data.

In the event of a personal data breach, the Principal Investigator informs the involved investigator site without undue delay after becoming aware of the breach. The involved investigator site shall notify the competent supervisory authority of the infringement without undue delay and, where possible, within 72 hours of becoming aware of it. Where the notification to the supervisory authority is not made within 72 hours, it shall be accompanied by the reasons for the delay. The notification should describe the nature of the personal data breach including the approximate number of subjects concerned, the contact details of the data protection officer, the likely consequences of the personal data breach and the measures taken or to be taken to fix the personal data breach and also, where appropriate, to mitigate its possible adverse effects. If the breach of personal data presents a high risk to the rights and freedoms of natural persons, the involved investigator site shall communicate in plain and clear language the nature of the breach to the data subject without undue delay, unless the data controller has made personal data incomprehensible to anyone who is not authorized to access it, or has subsequently adopted measures to avoid the occurrence of a high risk for the rights and freedoms of the subjects.

Clinical evaluation plan deviations

In the case of minor and isolated deviations from the protocol, these are recorded in the case report form, which is provided with a space to record any changes or comments the doctor deems appropriate (e.g. treatment not carried out, change of dressing applied, lack of a detection).

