Generalized linear models (GLM) will be used to investigate whether differences between the two groups are influenced in a confounding way by demographic and clinical covariates, pre-treatment measurement, and to measure their impact that will allow us to understand which variables affect the outcome and will also allow us to analyse the differences between groups being equal for these covariates.

A descriptive statistic of adverse events, if present, will also be made through tables with frequencies and percentages, and bar charts.

All significance tests will have a statistically significant p. value <0.05. The analysis will be carried out with the open source software R Commander (v. 2.2-0).

croData publication policy

At the end of the clinical study and of the related analysis about the obtained results, these will be made available anonymously and aggregated in full respect of the protection of the right to privacy, in accordance with Regulation no. 2016/679 (GDPR, General Data Protection Regulation), for publication in national or international journals, or for presentation by investigators at scientific conferences and in medical journals. For the writing of any publications concerning the study in question, may be used professional medical writers who will write manuscripts on behalf of the company and for which the company undertakes to ensure analogous compliance with current legislation.

After the conclusion of the study, the sponsor will be responsible for drawing up the final report of the clinical trial in the manner and timing prescribed in the current legislation regarding clinical investigations; external consultants of the sponsor, experts in this field, may be involved in the preparation of the final report and for which the sponsor ensure the same compliance with current legislation.

References

1. Clark R (1985) Cutaneous tissue repair: basic biological considerations. *J Am Acad Dermatol* 13: 701-725.
3. Nwomeh BCM Yager DR, Cohen IK (1998) Physiology of the chronic wound. *Clinics in Plastic Surgery* 25 (3): 341
4. Hackam DJ, Ford HR (2002) Cellular, biochemical and clinical aspects of wound healing. *Surgical Infections* 3: S23-S35.
5. Calderhead (2007), The photobiological basis behind light-emitting diode (LED) phototherapy, *Laser therapy*.

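### The safety endpoint counts only 'related' adverse events without saying related to what or judged by whom, in an unmasked trial whose described forms list no adverse-event item, so the arm counts will be hard to interpret

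*Combined protocol and SAP*

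**What the plan says.** Safety is part of the aim under Study Objectives and a secondary objective under Primary and secondary objectives. Its single endpoint, under Secondary endpoints, is "Safety of treatment (number of related adverse events in the two groups".

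The arms are described under Medical and surgical procedures and study follow-up. For controls, the text reads: "The Control Group will follow the standard treatment indicated three times a week for the 4 weeks of observation". The treated arm differs by the addition of the device: "The experimental group will undergo, in addition to the standard treatment, treatment with Emoled three times a week for 4 consecutive weeks". No sham is described, and the Bias section states that assignment cannot be masked.

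On data capture, the Case Report Forms section gives the content of the 'Patient Visit' form as "namely those relating to the parameters of the PUSH scale (size of the lesion, exudate and type of tissue), the dressings and any notes". The case report form itself is described by identifiers, allergies and lesion characteristics. Other routes appear elsewhere:

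- Ethical considerations promises that discomfort will be followed "through a special questionnaire on the detection of discomfort connected to participating in the study in question".
- The same section says that risk and benefit will be checked "taking into account any adverse events / device-related accidents or non-serious side effects reported by the main investigators".
- Clinical evaluation plan deviations mentions a case report form "which is provided with a space to record any changes or comments the doctor deems appropriate".

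The planned analysis, under Statistical analysis, is: "A descriptive statistic of adverse events, if present, will also be made through tables with frequencies and percentages, and bar charts".

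**The concern.** A between-arm count of events is informative only if an event has the same chance of being counted in each arm. Restricting the count to 'related' events puts a judgement between the event and the count. Here that judgement has no stated object, assessor or scale, and no masked assessor is provided for. One arm receives the device and the other does not, so the filter need not act equally on both.

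The error can run either way. Ordinary background events attributed to the device in treated patients would look like a device harm. A real excess that nobody recognises as a device effect would be dropped before the arms are compared. The first could discredit a harmless device; the second could support a claim of safety that was never tested. The introduction already rests part of its risk-benefit argument on the absence of recorded adverse events in previous studies, so how events are recorded here matters.

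**Working it through.** The plan states no figure for the safety endpoint, so there is none to reproduce. The check is a reading of the sections together, followed by arithmetic on the size of the possible artefact.

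**1. Inputs from the protocol.** Number of patients expected to enroll gives 10 per arm within each of two ulcer stages, so 10 + 10 = 20 per arm. Controls have no device. The significance level is 0.05; I take it as two-sided, since sidedness is not stated. No adverse-event rate is given for either arm, so all rates below are assumptions.

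**2. What 'related' can mean.** The Definitions under Accidents and their reporting cover device accidents and serious accidents, and define neither 'adverse event' nor 'related'. Two readings remain:

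- *Related to the device.* Controls are never exposed, so their count is 0 by construction and carries no information.
- *Related to any treatment or study procedure.* Controls can have events, since they too receive cleansing, dressings and possible debridement. The count still depends on an unspecified judgement made without masking.

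**3. Size of the artefact on the first reading.** Let q be the all-cause risk, equal in both arms, and s the share of treated patients with an event whose event is judged device-related, counting at most one event per patient. The expected related count is 20 × q × s against 0. Fisher's exact p for x of 20 against 0 of 20 is 2 × C(20,x)/C(40,x):

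- x = 4: 2 × 4,845/91,390 = 0.106
- x = 5: 2 × 15,504/658,008 = 0.047

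Thus 5 against 0 is enough to fall below 0.05. The chance of that is P(X ≥ 5) with X binomial (20, q × s):

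| Assumed q (both arms) | Assumed s | Expected counts | Chance of p < 0.05 |
|---|---|---|---|
| 20% | 50% | 2 vs 0 | 4% |
| 40% | 50% | 4 vs 0 | 37% |
| 60% | 50% | 6 vs 0 | 76% |

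The true all-cause difference is nil in every row. Counting all events instead, with equal risks of 20% to 60%, gives Fisher p < 0.05 in about 2.3% to 2.4% of trials. No safety test is planned, so these chances only gauge how misleading the table could look.

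**4. The opposite error.** Assume all-cause risks of 30% treated and 10% control: 20 × 0.30 = 6 patients against 20 × 0.10 = 2. If none of these events is judged related, the endpoint reads 0 against 0.

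**5. Endpoint against analysis.** The endpoint is limited to related events; the planned table is of adverse events without that limit. They are different quantities, and the plan does not say which will be reported.

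**6. Capture.** Neither form description lists an adverse-event item. What remains is free notes, data drawn from medical records, the comment space (described for minor deviations), the discomfort questionnaire (absent from the visit table and the form descriptions) and investigator reports with no form or schedule. Infection shows the consequence: the protocol foresees it during observation, but it is not a PUSH item and would surface only through a dressing change or a note.

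**7. What all-cause counting would give.** At 20 per arm, exact Fisher power is 24% for 10% vs 30%, 19% for 20% vs 40%, 41% for 20% vs 50% and 65% for 20% vs 60% (all assumed rates). With no events in 20 patients, the exact two-sided 95% upper limit is 1 − 0.025^(1/20) = 16.8%.

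**The case against.** The strongest reply is that the endpoint does not say device-related. Elsewhere the protocol names the device when it means it, as in "taking into account any adverse events / device-related accidents or non-serious side effects reported by the main investigators", and controls receive treatments to which events can be related. This stands. A reader might infer that the control count is zero by definition; the text supports that only on one of two readings. The defect is an undefined term.

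A reader might also infer that adverse events are not collected at all. The documents do not support that either. Recording of clinical data says endpoint data are taken at visits in both arms, notes and medical records feed the database, and monitoring checks completeness. The forms themselves are not in the documents, only a description of them. What stands is that no structured, scheduled capture is described.

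It would likewise be wrong to say that worsening wounds are filtered out. PUSH at every visit and lesion area from the photographs record worsening in both arms whatever its cause, and both are compared between arms. The gap concerns events outside those measures.

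The documents do not name who judges relatedness, so it cannot be asserted that the treating staff do; it can be said only that no masked assessor is provided for.

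Finally, this is a 40-patient proof of concept on a CE-marked device under post-market vigilance, with only a descriptive safety summary. That limits the consequences. But vigilance rules address device accidents and cannot supply a control-arm rate, and a descriptive table of non-comparable counts can still mislead.

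**Conclusion.** The point holds as one of specification and comparability. 'Related' has no stated object, assessor or scale; the trial is unmasked without a sham; the endpoint and the planned table disagree; and no adverse-event item is described on the forms. If 'related' means device-related, the control count is empty of information, and an expected 4 against 0 can arise from identical arms (assuming 40% risk and half judged related). On the wider reading the count is still filtered by unmasked judgement.

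It does not follow that the trial cannot address its safety objective: capture is unstructured, not absent, and wound worsening is measured. Nor does the 16.8% limit measure this defect, since it applies to any 0 of 20, before or after a change. It shows only that safety evidence from this trial will be modest in any case. Every event rate used here is an assumption, because the protocol gives none.

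**What to change.** - **Endpoint.** Redefine it as the number and percentage of patients with any adverse event, whatever the cause, from V1 to V12 in each arm.
- **Relatedness.** Show it as a secondary column, separately for the device and for the dressing or standard treatment, with a stated assessor and causality scale. Report device-related events for the treated arm only.
- **Analysis.** Align the sentence on adverse events under Statistical analysis with the new endpoint and keep it descriptive.
- **Form.** Add a yes/no adverse-event item to the 'Patient Visit' form at all 12 visits in both arms.

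The cost is a revised endpoint sentence, a matching analysis sentence and one form item: at most 40 × 12 = 480 entries, at visits already scheduled. The downside is that more unrelated events will be recorded in a frail inpatient population. The change makes the arms comparable; it does not give the trial power to detect safety differences.

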The safety and efficacy clinical validation to obtain the CE marking for the EmoLED device for the treatment of acute surgical wounds is ongoing. In particular, the acute observations, whose detailed results are provided in the attached final Report on the clinical trial, have once again demonstrated the device's safety and efficacy in shortening the healing time of spontaneously healing wounds. Isolated observations in patients with chronic lesions, of various aetiologies, have shown that the device is capable of unblocking the healing process, thus allowing the wound to progress beyond the inflammatory phase by inducing re-epithelialisation and wound closure. Observations made using a thermal camera have also shown that, due to the compromised condition of the tissues surrounding the ulcers, the baseline temperature of the limb is lower than normal and that both during and after treatment with the EmoLED device, the temperature never exceeds 40°C.

Information related to the clinical investigation

Study description

The commercial purpose of this study is to value the clinical efficacy of a battery-powered device that uses blue LEDs.

The study aims to compare the response of an existing standard treatment for second and third stage pressure sores, with a protocol that plans the administration of the EmoLED treatment three times a week for 4 consecutive weeks in addition to the conventional therapy.

Primary and secondary objectives

The primary objective of the study will be to assess the clinical efficacy of a treatment made through a battery-powered portable medical device that uses blue LEDs, in addition to the conventional therapy, applied on second and third degree pressure sores, compared to the conventional treatment alone, at the end of the fourth week of observation. As secondary objectives, the study proposes the clinical evaluation of lesions during the 4 weeks of treatment, and the evaluation of the treatment’s safety.

Endpoints

Primary endpoint of the study

The primary endpoint of the study is the assessment of the clinical state of second and third stage ulcers by reducing the index of the PUSH scale, in the two treatment groups at the end of the 4-week observation period.

Secondary endpoints

1. The assessment, during the weeks of observation, of the percentage of reduction of the lesion area compared to V0 in the second and third stage lesions in the two treatment groups;

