If the patient has two or more decubitus lesions at the same stage, the doctor will choose to treat the lesion of which, in his opinion, the data acquisition (photography and size measurement) is better. If a patient has two or more lesions of different stages, the doctor will decide to include in the study only one of them, based on the number of lesions inserted at that time in the two groups, choosing the group with a smaller number: In this way, attempts are made to ensure a numerical trend as simultaneous as possible in the two groups of lesions (e.g. if the number of 2°stage lesions enlisted is less than the number of 3°stage lesions enlisted, then the 2°stage lesion will be included in the study). In the case of a numerical parity of the two groups of lesions, the doctor will decide to treat the lesion with a position that allows a better data acquisition (photographic image, measurement, etc.).

Case Report Forms

Case Report Forms are unique to every patient. It will be used the form of injury assessment already present at the Investigator Centre; the data collection by the Principal Investigator includes: patient's name and surname, date of birth, room number, medical record number, date of surgery, any allergies and the characteristics of the lesion under investigation -position and degree of the lesion-. Another section dedicated to the characteristics of the lesion, includes: dimensions (length x width), the amount of exudate and the type of tissue. All these features will be evaluated, according to the criteria of the international scale PUSH, with a score, specified in the legend in the form, of which the total will be reported at each visit.

The Pressure Ulcer Scale for Healing (PUSH) is a tool designed by the National Pressure Ulcer

Advisory Panel (NPUAP) and used to observe the trend of pressure ulcers over time, classifying them regarding the area of extension, the exudate and the tissue type, noting the partial score for each characteristic of the ulcer and summing those scores to obtain the total. Comparing the relevant total scores over time will provide an indication of the improvement or worsening of the healing of the pressure ulcer.

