During the 4 weeks of observation, once a week, concomitantly with the visit, and during the last visit (V12), a photographic image of the wound will be collected in order to be able to assess both qualitatively and quantitatively the progress of healing. The images will be collected with a portable device suitable for taking photographs (eg. tablet).

The acquisition of the photographic image will take place after any cleansing / debridement of the wound, before treatment with EmoLED / bandage.

Each photograph will be named with the patient code and the date of the visit. The photo shall cover

the entire area of the lesion. Next to the lesion will be placed a special ruler for the measurement of the area of the lesion.

Guidelines for photos' standardization

In order to have accurate measurements it is necessary that the image registration procedure is standardized.

The wound must be well focused and framed frontally; in all the photos the ruler with the patient's identification code must appear and the date and must be in focus so as to have the 1 mm scale reference. The operator should try to take the picture by fully framing the wound (preferably considering a margin around the wound), and position themselves so that the ruler is always present in the frame.

It is also advisable to avoid artifacts from the movement of the subject or operator, as they cause blurring and therefore make it difficult to correctly view the ruler or the wound.

Bias

The staff participating in the study will be trained on the correct use of the device and accessories, as well as on the correct execution of the clinical protocol and on the compilation of the associated forms.

The EMOLED staff is always at the team's disposal for any clarification or doubt during the study.

In order to avoid bias during the procedure for the assignment of the patients enrolled to the experimentation group, it should be noted that the randomization grid is not distributed to the investigators: instead, opaque and sealed envelopes are distributed that inside have an adhesive label with the patient's ID and their attribution group that reflects the randomization grid. This adhesive label must be glued on the patient folder containing the informed consent and the Case Report Form.

Since this is an experiment with a medical device that emits blue light, in this case the masking of the assignment to one of the two groups cannot be carried out.

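### The primary PUSH score is rated at visits with no masked assessor, and masking of the photographic measurement that could check its size component is not assured

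*Combined protocol and SAP*

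**What the plan says.** The section Primary endpoint of the study assesses the ulcers "by reducing the index of the PUSH scale, in the two treatment groups at the end of the 4-week observation period". Under Case Report Forms, the PUSH total is built from "dimensions (length x width), the amount of exudate and the type of tissue" and is recorded at every visit.

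On who scores and when, Recording of clinical data states: "Data related to the evaluation of the endpoints are acquired during the visit for both study groups". Case Report Forms names the Principal Investigator for data collection and describes an electronic visit form holding the PUSH parameters, one of three forms "which will be filled by the health care personnel of the study team of the Experimental Center".

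On masking, the Bias section describes staff training and sealed opaque envelopes, then says "in this case the masking of the assignment to one of the two groups cannot be carried out". The envelope holds a label with patient ID and group, taken from the randomization grid. "This adhesive label must be glued on the patient folder containing the informed consent and the Case Report Form".

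On photographs, the schedule under Measurable parameters places them at V1, V4, V7, V10 and V12, and at healing if that comes first. They are taken after cleansing and before that day's device treatment or bandage, with a 1 mm scale in frame. "Each photograph of the lesions will be identified only with the patient code and the date of the visit". The photo guidelines also require code and date to appear on the ruler inside the picture. "The analysis of the photographic images will be performed through an appropriate analysis algorithm", giving a surface in mm². Percentage area reduction is listed only under Secondary endpoints.

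**The concern.** Masking the treatment and masking the measurement are separate matters. Visible blue light explains why patient and operator cannot be masked. It does not explain why someone reading a photograph taken before that day's treatment cannot be.

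PUSH involves judgement, particularly for exudate and tissue type. If scorers lean slightly towards the device, the lean is indistinguishable from a treatment effect. Randomisation, the Mann-Whitney test and the planned covariate models cannot remove it, because it arises after allocation and follows the arm. The Statistics section says the results may inform the sample size of later studies, so an inflated effect would carry forward.

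**Working it through.** **1. Does the scorer know the arm?** No sentence says so outright. Four facts point that way: scoring takes place at the visit; the study team enters the PUSH parameters; the group label is on the folder holding the CRF; and no masked assessor is described. The inference is strong.

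**2. Is the image measurer masked?** The plan does not say who runs the algorithm. The photograph carries no arm. It does carry the patient code, and the randomization grid ties patient ID to group, so the code is a key to the arm for anyone with the grid or the folder. The date also shows visit order. Masking is therefore not assured. Renaming the file would not suffice, because code and date are also on the ruler.

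**3. What can a photograph replace?**

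| PUSH component | Available from a masked photograph? |
|---|---|
| Size (length x width) | Yes, read against the 1 mm ruler; the algorithm is described only as giving area |
| Exudate | Not reliably, since the image follows cleansing |
| Tissue type | Possibly; not assumed here |

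**4. How much could a scoring lean matter?** The plan has no power calculation to reproduce, and it gives neither an SD for PUSH nor any size of bias. What follows is an assumption-based range.

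Inputs: 10 per arm in each of two stages, so 2 x 10 = 20 per arm; Mann-Whitney; p < 0.05, taken as two-sided. Assumed: normal scores, no true effect, and a constant shift b in favour of the device, in SD units of PUSH change, acting on the whole score. Simulation, 20,000 runs:

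| b (SD) | P(p<0.05), 20 per arm | P(p<0.05), 10 per arm |
|---|---|---|
| 0 | 5.2% | 4.4% |
| 0.1 | 6.2% | 4.6% |
| 0.25 | 11.5% | 7.4% |
| 0.5 | 32.2% | 15.8% |

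Check by normal approximation, Φ(b/√(2/n) − 1.96), with n = 20 and √(2/20) = 0.316:
- b = 0.25: Φ(0.79 − 1.96) = Φ(−1.17) = 12.1%
- b = 0.5: Φ(1.58 − 1.96) = Φ(−0.38) = 35.2%

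This formula is for a comparison of means, so slightly higher values are expected. With whole-number scores and an assumed SD of 2 to 4 points, an average lean of one point is 1/4 = 0.25 to 1/2 = 0.5 SD; a simulation of that case gave 11-31%.

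**5. How much of that could masked size remove?** If a share s of the bias sits in size, b(1 − s) remains. For b = 0.5:
- s = 1/2 leaves 0.25 SD, about 11.5%.
- s = 1/3 leaves 0.33 SD, about 16-17%.

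Both shares are assumptions. The rate returns to 5% only if no bias is left in exudate and tissue type.

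**The case against.** **Proof of concept.** The sponsor can say that this is a small exploratory study, that lesion area is already a named outcome tested in the same way as PUSH, and that size is arguably the least subjective component. This stands in part and limits the gain. It does not answer the gap, because the area measurement is the natural check on the primary result and its own masking is unspecified.

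**Replacing bedside size inside the primary score.** A reader might infer that this should be done. The design does not favour it. PUSH is scored at 12 visits and photographed at five, so the size method would change from visit to visit within the Friedman analysis. With LOCF, a patient leaving after V8 could have a photographic baseline and a bedside final value.

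**The image measurer is unmasked.** A reader might also infer this from the sponsor's access to the electronic forms. The listed contents of those forms do not include the arm, and the operator is not named. The documents support only that masking is not assured.

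**The 12-32% range as the benefit of the fix.** It is not. It describes an assumed bias in the whole score, of which size is one part.

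**Conclusion.** The concern holds as a design weakness that should be addressed. The stated reason for not masking does not extend to measurement, and the plan leaves unused a record of the same lesion at the primary time point that could be read masked.

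The documents show a risk. They do not show that scores have been or will be biased, nor that the risk is wholly avoidable, since exudate and tissue type stay with site raters. Under an assumed lean of 0.25 to 0.5 SD, the false-positive rate of the 20-per-arm comparison would be about 12-32% instead of 5%, and about 7-16% within a single stage. These figures rest on assumed bias sizes, normal scores and no true effect.

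**What to change.** 1. **Mask the images before measurement.** Give each a random number, and crop or cover the code and date on the ruler while keeping the 1 mm scale. Whoever runs the algorithm should have no access to the randomization grid, CRF folder or visit forms.
2. **Keep bedside PUSH as the primary endpoint and pre-specify a sensitivity analysis.** Recompute PUSH change from V1 to V12 (or to the last or healing photograph), taking the size component from length and width read on the masked image at both time points and scored with the form's own legend. Never mix bedside and photographic size within one patient's change score. Let the masked reader decide which images are unreadable. The secondary endpoint refers to V0, which is not in the V1-V12 schedule, so the baseline label needs reconciling.
3. **Present this analysis and the masked area reduction beside the primary result.** State in advance that a benefit seen only in bedside PUSH, and not in the masked size measures, cannot be separated from observer bias. This is a statement on interpretation: a real effect confined to exudate or tissue type could look the same.

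Cost: a relabelling and cropping step on up to 5 x 40 = 200 scheduled images already due for measurement, and a length and width reading on two per patient (2 x 40 = 80). No added visits, staff or patient procedures. Some images will be unreadable, and exudate and tissue type remain unmasked.
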